3.2 Exclusion Criteria

- Patients with corneal dystrophies, including anterior basement membrane dystrophy, keratoconus, and Fuch's endothelial corneal dystrophy.
- Age < 18 years
- Pregnant women
 - Cognitive impairment
- Prisoners

3.3 Early Withdrawal of Subjects

3.3.1 Criteria for removal from study

Subjects may withdrawal from the study if they no longer wish to participate in the study.

Subjects may withdrawal from the study if they no longer plan to undergo femtosecond laser-assisted cataract surgery with astigmatic keratotomy. There are no anticipated safety reasons for which a subject would need to withdrawal from the study. There is no disease progression that would require a subject to withdrawal from the study.

3.3.2 Follow-up for withdrawn subjects

Subjects may withdrawal from the study at any point up to their post-operative one-month exam. Data will be collected for the number and the reason for withdrawal of subjects (eg. withdrawal of consent). A patient disposition flow diagram will be constructed. Subjects that withdrawal from investigational treatment will be treated as any other patient who is undergoing cataract surgery outside of the study.

4.0 Recruitment Methods

4.1 Identification of subjects

Participants will be identified by [name] during a scheduled patient clinic visit to review the medically planned femtosecond laser-assisted cataract surgery with astigmatic keratotomy standard of care cataract surgery consent.

4.2 Recruitment process

All eligible patients will be offered the opportunity to participate in the research study. The [name] will explain the research study to potential subjects at their pre-surgery clinic visit.

4.3 Recruitment materials

None

4.4 Eligibility/screening of subjects

Not applicable

5.0 Consent Process and Documentation

5.1 Consent Process

5.1.1 Obtaining Informed Consent

5.1.1.1 Timing and Location of Consent

Informed consent is a process. Consent will take place in the ophthalmology clinic when a patient would be regularly consented to undergo cataract surgery (within 60 days of surgery date). As the patient presents for surgery, the consent will be reviewed once again and any additional questions will be addressed to confirm they still want to participate in the study.

5.1.1.2 Coercion or Undue Influence during Consent

Subjects will be informed that participation is voluntary and that their decision will not affect their care. Physician investigators will discuss the study with the patients and answer all questions.

5.1.2 Waiver or alteration of the informed consent requirement

A waiver of consent is requested to review medical record information to determine preliminary eligibility to participate in the research.

5.2 Consent Documentation

5.2.1 Written Documentation of Consent

The consent process will be documented in writing with the long form of consent documentation:

- The current IRB approved consent form will be obtained.
- We will verify that we are using the most current IRB-approved version of the study specific consent form and that the consent form is in language understandable to the subject.
- A copy of the consent form will be provided to the subject. Whenever possible the consent form will be provided to the subject in advance of the consent discussion.

5.2.2 Waiver of Documentation of Consent (Implied consent, Verbal consent, etc.)

Not applicable

5.3 Consent – Other Considerations

5.3.1 Non-English Speaking Subjects

Not applicable

5.3.2 Cognitively Impaired Adults

5.3.2.1 Capability of Providing Consent

Not applicable

5.3.2.2 Adults Unable To Consent

Not applicable

5.3.2.3 Assent of Adults Unable to Consent

Not applicable

5.3.3 Subjects who are not yet adults (infants, children, teenagers)

5.3.3.1 Parental Permission

Not applicable

5.3.3.2 Assent of subjects who are not yet adults

Not applicable

6.0 HIPAA Research Authorization and/or Waiver or Alteration of Authorization

6.1 Authorization and/or Waiver or Alteration of Authorization for the Uses and Disclosures of PHI

Check all that apply:

- Not applicable, no identifiable protected health information (PHI) is accessed, used or disclosed in this study. [Mark all parts of sections 6.2 and 6.3 as not applicable]
- Authorization will be obtained and documented as part of the consent process. [If this is the only box checked, mark sections 6.2 and 6.3 as not applicable]
- Partial waiver is requested for recruitment purposes only (Check this box if patients' medical records will be accessed to determine eligibility before consent/authorization has been obtained). [Complete all parts of sections 6.2 and 6.3]
- Full waiver is requested for entire research study (e.g., medical record review studies). [Complete all parts of sections 6.2 and 6.3]
- Alteration is requested to waive requirement for written documentation of authorization (verbal authorization will be obtained). [Complete all parts of sections 6.2 and 6.3]

6.2 Waiver or Alteration of Authorization for the Uses and Disclosures of PHI

6.2.1 Access, use or disclosure of PHI representing no more than a minimal risk to the privacy of the individual

6.2.1.1 Plan to protect PHI from improper use or disclosure

Information is included in the "Confidentiality, Privacy and Data Management" section of this protocol.

6.2.1.2 Plan to destroy identifiers or a justification for retaining identifiers

Study information will be destroyed after the research has ended and all institutional/regulatory requirements for data retention have been met.

6.2.2 Explanation for why the research could not practically be conducted without access to and use of PHI

Information must be obtained from the subject's electronic medical record during recruitment to determine eligibility and, in some cases, to confirm information discussed with the subject in regards to their medical history.

6.2.3 Explanation for why the research could not practically be conducted without the waiver or alteration of authorization

The waiver is requested only for recruitment to determine subject eligibility to ensure that no medical conditions that fall into the exclusion criteria are present and would thus preclude enrollment. This waiver will minimize the enrollment of subjects' who may ultimately fail to meet the study inclusion/exclusion criteria.

6.3 Waiver or alteration of authorization statements of agreement

Protected health information obtained as part of this research will not be reused or disclosed to any other person or entity, except as required by law, for authorized oversight of the research study, or for other permitted uses and disclosures according to federal regulations.

The research team will collect only information essential to the study and in accord with the 'Minimum Necessary' standard (information reasonably necessary to accomplish the objectives of the research) per federal regulations.

Access to the information will be limited, to the greatest extent possible, within the research team. All disclosures or releases of identifiable information granted under this waiver will be accounted for and documented.

7.0 Study Design and Procedures

7.1 Study Design

This is a prospective cohort study of patients who are undergoing femtosecond laser-assisted cataract surgery with astigmatic keratotomy. Patients will be selected to participate in the study based on inclusion/exclusion criteria.

It should be noted that this is an observational, not interventional study. The parameters to be chosen for the femtosecond AKs will be determined using best practices (surgeon's choice using algorithms created for manual LRIs but adapted for use with the laser). Whether a patient is enrolled in the study or not will not influence the architecture or plan for the femtosecond AKs. The purpose of the study is to carefully examine the effects of these femto AK on corneal astigmatism in a retrospective fashion (after the 1 month post-operative visit) so that a nomogram can be developed using regression analysis. As such, the only 'intervention' patients enrolled in the study will receive that un-enrolled patients will not is measurement of corneal hysteresis and corneal biometry at their 1 month post-operative visit.

7.2 Study Procedures

7.2.1 Visit 1 or Day 1 or Pre-test, etc. (format accordingly)

Pre-operative visit: Inclusion/exclusion criteria will be assessed. Consent will be obtained from eligible subjects who wish to participate in the study. Demographic and baseline characteristics will be recorded. Pre-operative biometry, refraction, and corneal hysteresis data will be collected.

7.2.2 Visit 2

Day of surgery: Data from the femtosecond laser will be collected, including the various laser parameters that are used to make the astigmatic keratotomies and clear corneal incisions.

7.2.3 Visit 3

Day of surgery for contralateral eye: Data from the femtosecond laser will be collected, including the various laser parameters that are used to make the astigmatic keratotomies and clear corneal incisions.

7.2.4 Visit 4 or post-operative month #1 visit (1 month after 2nd operative procedure)

Post-operative month 1 visit: One-month post-operative IOL master, autorefraction, manifest refraction, and uncorrected visual acuity will be collected.

7.3 Duration of Participation

The individual subject will participate in the study from the time consent is obtained at their pre-operative visit, through their femtosecond laser-assisted cataract surgery with astigmatic keratotomy on both eyes, and until their one-month post-operative visit.

8.0 Subject Numbers and Statistical Plan

8.1 Number of Subjects

300

8.2 Sample size determination

Eyes may have with-the-rule, against-the-rule, and oblique astigmatism. Corneas with varying forms of astigmatism will respond differently to the AKs; thus it is necessary to have a sufficient number of eyes to produce results for all forms of astigmatism. Approximately 50% of eyes have against-the-rule astigmatism, 30% with-the-rule, and 20% oblique. 20% of 300 eyes = 60, which was felt to be the minimum number to produce meaningful results for this group.

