3.0 Inclusion and Exclusion Criteria

3.1 Inclusion Criteria

- Age: ≥18 years of age
- Sex: male or female
- Patients who are planned to undergo femtosecond laser-assisted cataract surgery with astigmatic keratotomy at the Schein Ernst Mishra Eye clinic within the next 60 days of their cataract consultation visit. Subjects with planned single or bilateral cataract eye surgeries are eligible. Planned opposite eye surgery must be within 2-4 weeks of first cataract surgery.
- Fluent in written and spoken English

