8.3 Statistical methods

Eyes that do not obtain a final best-corrected visual acuity of 20/40 or better will be excluded from the final data analysis. Mean change in keratometric astigmatism will be determined by subtracting preoperative astigmatism from postoperative mean astigmatism. Vector analysis and double-angle plot will be used to analyze aggregate astigmatism. We will require assistance from a statistician.

A sub-group analysis will likely include patients that had prior refractive surgery (i.e. LASIK).

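### On section 8.2's basis of 300 eyes, the 60 oblique eyes called the minimum are only the expected count before any loss; if 300 means subjects, the outcome depends on an unstated bilateral share

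*Combined protocol and SAP*

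**What the plan says.** Section 8.2 argues that the forms of astigmatism respond differently to the incisions, so each form needs enough eyes. It gives the mix as "Approximately 50% of eyes have against-the-rule astigmatism, 30% with-the-rule, and 20% oblique" and concludes: "20% of 300 eyes = 60, which was felt to be the minimum number to produce meaningful results for this group". No other quantitative reason for the sample size is given.

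Two other sections remove data before the analysis:

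- Section 3.3.2: "Subjects may withdrawal from the study at any point up to their post-operative one-month exam".
- Section 8.3: "Eyes that do not obtain a final best-corrected visual acuity of 20/40 or better will be excluded from the final data analysis".

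The endpoints in sections 1.2 and 1.3 are all collected at month one, so an eye lost before that visit contributes nothing to them. Neither a withdrawal rate nor a 20/40 failure rate is stated, and the 300 is not inflated for either.

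The unit is also unsettled. Section 8.1, headed "8.1 Number of Subjects", gives 300, whereas 8.2 counts 300 eyes. Section 3.1 states: "Subjects with planned single or bilateral cataract eye surgeries are eligible". Section 7.3 describes participation "through their femtosecond laser-assisted cataract surgery with astigmatic keratotomy on both eyes". The expected share of bilateral subjects appears nowhere.

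**The concern.** A figure called a minimum should be one that the design has a good chance of reaching. In 8.2 the minimum and the expected count are the same number. Even with complete data, the actual count would then fall short about half the time. Any loss of eyes moves the expected count below the minimum, and the plan itself provides for such losses. No quota or stratified enrolment protects the oblique group; section 4.2 offers participation to all eligible patients.

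Oblique eyes set the sample size because they are the smallest group, and the nomogram in section 1.1 is meant to guide incision location and arc length. If 8.2 stands as written, a reader of the results could take the oblique group to have been planned with a secure 60 eyes, when on that section's own basis 60 is a midpoint before loss.

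**Working it through.** **Inputs.** From 8.2: 300 eyes, oblique share 20% (approximate), minimum 60. From 8.1: 300 subjects. From 3.1: one or two eyes per subject. Assumed here, because the documents give no figures: the loss rates and the bilateral shares. Loss means withdrawal and the 20/40 exclusion combined, taken as equal across astigmatism types.

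**Step 1, the plan's figure.** 0.20 × 300 = 60. It reproduces exactly; the arithmetic in 8.2 is right.

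**Step 2, chance variation with no loss.** With eyes independent, the oblique count is Binomial(300, 0.20). Its mean is 60 and its SD is √(300 × 0.20 × 0.80) = 6.93. The 2.5% and 97.5% quantiles are 47 and 74. P(count < 60) = 0.477.

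**Step 3, loss, if 300 is the number of eyes enrolled.** Analysable eyes n = 300 × (1 − loss), and the oblique count is Binomial(n, 0.20).

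| Assumed loss | Analysable eyes | Expected oblique | P(below 60) |
|---|---|---|---|
| 0% | 300 | 60 | 0.48 |
| 1% | 297 | 59.4 | 0.51 |
| 5% | 285 | 57 | 0.65 |
| 10% | 270 | 54 | 0.80 |
| 15% | 255 | 51 | 0.91 |

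If each eye is instead lost at random, so that the count is Binomial(300, 0.20 × (1 − loss)), the last three probabilities become 0.65, 0.80 and 0.90. The choice of model hardly matters.

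**Step 4, if 300 is the number of subjects.** Eyes = 300 × (1 + bilateral share). At an assumed 10% loss, the expected oblique count is eyes × 0.20 × 0.90. The chance of reaching 60 is given first with fellow eyes independent, then with fellow eyes always of the same type and lost together.

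| Assumed bilateral share | Eyes | Expected oblique | P(at least 60), independent | P(at least 60), concordant |
|---|---|---|---|---|
| 10% | 330 | 59.4 | 0.49 | 0.49 |
| 25% | 375 | 67.5 | 0.86 | 0.82 |
| 50% | 450 | 81 | 0.997 | 0.98 |
| 100% | 600 | 108 | above 0.999 | above 0.999 |

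The expected count stays at 60 or more if eyes per subject are at least 1 / (1 − loss): 1.11 at 10% loss and 1.25 at 20%.

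**Step 5, sensitivity to the 20% share.** With 300 eyes and no loss, P(at least 60) is 0.20 if the true share is 18% and 0.82 if it is 22%, against 0.52 at 20%.

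**The case against.** The strongest reply concerns the unit. A reader might infer that the study will probably miss its minimum. The documents do not support that as a general statement. Section 8.1 gives 300 as subjects, section 3.1 admits bilateral surgery, section 7.2.3 schedules a visit for the second eye, and section 7.3 speaks of both eyes. With a moderate bilateral share, reaching 60 is likely (Step 4). This reply stands, and it makes the point conditional. It does not remove the point, because 8.2 does its calculation in eyes and claims no surplus from second eyes.

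A second reply is that the loss rates are not the plan's. That is correct. On the plan's own figures alone the chance of a shortfall is 48%, slightly under even. On the eyes basis, however, about 1% loss is enough to pass even odds.

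A third reply is that 8.2 never calls the 60 eyes guaranteed or analysable. It says only that the number "which was felt to be the minimum number to produce meaningful results for this group". That also stands: there is no guarantee in the text to withdraw. Nor do the documents show that a few eyes under 60 would be inadequate, since no effect size, SD or power value lies behind the number. Precision varies with √n, so falling from 60 to 57, 54 or 51 widens a confidence interval by about 3%, 5% or 8% (√(60/57) = 1.026, √(60/54) = 1.054, √(60/51) = 1.085). The practical loss is small. What remains is that the plan's only sizing argument presents an expected count before loss as a minimum.

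**Conclusion.** The point holds conditionally. If 300 is the number of eyes, as 8.2 has it, 60 is the expected oblique count before loss. The shortfall probability is then 48% with none lost, rising to 65%, 80% and 91% at an assumed 5%, 10% and 15% loss. If 300 is the number of subjects, whether 60 is reached depends on a bilateral share that the plan does not give. At an assumed 10% loss the break-even share is about 11%, and at 25% or more the minimum is likely to be met.

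These figures rest on a true oblique share of 20%, on loss unrelated to astigmatism type and, except in the concordant column of Step 4, on independent eyes. Agreement in type between fellow eyes would widen the 47 to 74 range. Two stronger readings are not supported: that the design will probably fall short whatever the unit, and that oblique results would be inadequate below 60. This is a missing allowance and an unresolved unit, not an arithmetic error.

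**What to change.** Reconcile 8.1 and 8.2 so that both say whether 300 counts eyes or subjects, and whether it is the number enrolled or the number evaluable. Then restate 8.2 with three stated assumptions: the bilateral share, the combined loss rate from withdrawal and the 20/40 rule, and the oblique share. The sponsor should supply these from its own clinic experience; the 5% to 15% used here is only illustrative.

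Give the oblique figure as an expected analysable number with its range. If 300 is eyes, say that the count may fall below 60. If 300 is subjects, derive the expected eyes as 300 × (1 + bilateral share) before applying loss, and note that agreement between fellow eyes widens the range.

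The cost is a rewording of 8.1 and 8.2. No added enrolment is needed. The rewording does not secure 60 oblique eyes; it states what the design can be expected to deliver. The downside is a slightly less favourable stated figure if 300 turns out to mean eyes.

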8.3 Statistical methods

Eyes that do not obtain a final best-corrected visual acuity of 20/40 or better will be excluded from the final data analysis. Mean change in keratometric astigmatism will be determined by subtracting preoperative astigmatism from postoperative mean astigmatism. Vector analysis and double-angle plot will be used to analyze aggregate astigmatism. We will require assistance from a statistician.

A sub-group analysis will likely include patients that had prior refractive surgery (i.e. LASIK).

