1.0 Objectives

1.1 Study Objectives

1. To determine the degree of surgically induced astigmatism of femtosecond laser clear corneal incisions
2. To determine the post-operative mean reduction in keratometric astigmatism and uncorrected distance visual acuities in patients undergoing femtosecond laser-assisted cataract surgery with astigmatic keratotomy (AK)
3. To determine the role of corneal biomechanics (hysteresis) on AK calculations.
4. To develop a nomogram that may be utilized in determining location and arc length of AKs for femtosecond laser-assisted cataract surgery with astigmatic keratotomy

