1.2 Primary Study Endpoints

The primary outcome measures are as follows (collected at post-operative month one):

- Uncorrected visual acuity
- Post-operative corneal curvature measurements and astigmatism as assessed using optical biometer
- Post-operative auto-refraction

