1.3 Secondary Study Endpoints

The secondary outcome measures are as follows (collected at post-operative month one):

- Mean change in astigmatism in eyes with ‘with the rule’ (WTR) astigmatism
- Mean change in astigmatism in eyes with ‘against the rule’ (ATR) astigmatism
- Complications related to placement of femtosecond laser AKs

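### Section 8.3 removes eyes from the whole final analysis on a post-operative result (best-corrected acuity worse than 20/40), which flatters uncorrected acuity, can understate AK complications and discards usable keratometry

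*Combined protocol and SAP*

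**What the plan says.** Section 8.3 sets the rule: "Eyes that do not obtain a final best-corrected visual acuity of 20/40 or better will be excluded from the final data analysis". It gives no reason and limits the rule to no endpoint. No other section narrows it, adds an analysis of all eyes, or defines a separate population for complications.

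The rule touches these parts of the plan:

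- **Objective 2 (section 1.1)** concerns the reduction in keratometric astigmatism and "uncorrected distance visual acuities in patients undergoing femtosecond laser-assisted cataract surgery with astigmatic keratotomy".
- **Primary endpoints (section 1.2)**, taken at month 1, include "Uncorrected visual acuity" and astigmatism from the optical biometer.
- **Secondary endpoints (section 1.3)** include "Complications related to placement of femtosecond laser AKs".
- **Exclusion criteria (section 3.2)** name only one class of eye disease: "Patients with corneal dystrophies, including anterior basement membrane dystrophy, keratoconus" and Fuchs' dystrophy. Nothing is said about retinal or optic nerve disease, or about visual potential.
- **Month-1 visit (section 7.2.4)**: "One-month post-operative IOL master, autorefraction, manifest refraction, and uncorrected visual acuity will be collected". Best-corrected acuity (BCVA) is not named.
- **Disposition (section 3.3.2)**: "Data will be collected for the number and the reason for withdrawal of subjects", with a flow diagram of patients. Eyes removed under section 8.3 are not mentioned.

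**The concern.** The rule selects eyes on an outcome. Objective 2 is about patients who have the operation, not the subset who later turn out to see 20/40 with correction. The consequences differ by endpoint.

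- **UCVA.** The removed eyes are those with the worst acuity, so the reported result describes a more favourable group than the cohort in Objective 2.
- **Complications.** An AK complication severe enough to hold BCVA below 20/40 takes its own eye out of the count.
- **Keratometry and nomogram.** The change score and the vector analysis need astigmatism before and after surgery, not BCVA. An eye limited by, say, retinal disease can enrol, give valid biometry and then be discarded. That costs data and narrows the range of eyes to which the nomogram applies. It does not by itself bias the nomogram in a known direction, because BCVA is measured with refractive error corrected.

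**Working it through.** **Inputs.** The documents give 300 as the sample size and 20% as the oblique share (sections 8.1 and 8.2). They do not give the fraction of eyes excluded (f), the true share with UCVA of 20/40 or better (p), a UCVA success threshold, or a complication rate (c). Values for these are assumptions. The share at 20/40 or better is a convenient summary, not a protocol endpoint.

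**1. The plan's own figure.** 0.20 × 300 = 60 oblique eyes, the number section 8.2 treats as the minimum. It reproduces. No power calculation is given, so there is none to check.

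**2. Share with UCVA of 20/40 or better.** If no eye sees better uncorrected than best-corrected, every excluded eye is a failure at 20/40. The successes stay and the denominator shrinks, so the reported share is p/(1 − f).

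| True p | f = 2% | f = 5% | f = 10% |
|---|---|---|---|
| 60% | 0.60/0.98 = 61.2% | 0.60/0.95 = 63.2% | 0.60/0.90 = 66.7% |
| 80% | 0.80/0.98 = 81.6% | 0.80/0.95 = 84.2% | 0.80/0.90 = 88.9% |

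For scale, the 95% confidence half-width for 80% in 300 independent eyes is 1.96 × √(0.8 × 0.2/300) = 4.5 points. At p = 80% the shift is 1.6, 4.2 and 8.9 points.

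**3. Mean UCVA.** The all-eye mean minus the retained mean equals f × (mean of excluded − mean of retained). With an assumed gap of 0.3 to 0.6 logMAR:

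- f = 2%: 0.006 to 0.012
- f = 5%: 0.015 to 0.03
- f = 10%: 0.03 to 0.06

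At 0.02 logMAR per letter this is about 0.3 to 3 letters.

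**4. Complication rate.** Let complicated eyes be R times as likely to be excluded as the others. Then e0 = f/(cR + 1 − c), e1 = R × e0, and the reported rate is c(1 − e1)/(1 − f). With c = 3%:

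| R | f = 5% | f = 10% |
|---|---|---|
| 1 | 3.00% | 3.00% |
| 3 | e1 = 0.1415, reported 2.71% | e1 = 0.2830, reported 2.39% |
| 5 | e1 = 0.2232, reported 2.45% | e1 = 0.4464, reported 1.85% |

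There is no bias when R = 1. Understatement needs complicated eyes to be excluded more often than others.

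**5. Oblique eyes.** If 300 means eyes, as in section 8.2, 60 × 0.95 = 57 remain at f = 5% and 60 × 0.90 = 54 at f = 10%. If 300 means subjects, as in section 8.1, second eyes can make up the loss, since "Subjects with planned single or bilateral cataract eye surgeries are eligible". Keeping 60 needs 60/(0.2 × 0.95) = 315.8, so 316 eyes (16 second eyes, 5.3% of 300), or 60/(0.2 × 0.90) = 333.3, so 334 eyes (34 second eyes, 11.3%).

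**The case against.** **The rule has a sensible purpose and is set in advance.** The study wants a nomogram for corneal astigmatism, with spectacle independence as the clinical aim. UCVA says little about astigmatism correction in an eye limited by other disease. This stands, and it supports a restricted UCVA analysis. It does not support removing those eyes from keratometry or complications, or leaving the all-eye UCVA result unreported.

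**The sentence may be meant only for the methods that follow it.** Section 8.3 goes on to keratometric change and vector analysis and gives no method for complications. That reading is possible, but the text refers to the final data analysis without qualification. Section 8.3 gives no method for UCVA either, so the narrow reading would confine the rule to keratometry, which does not use BCVA.

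**Poor BCVA may mark unreliable keratometry.** This is true of some eyes, since corneal problems other than dystrophies can enter and prior refractive surgery is expected. A measurement-quality criterion deals with that directly; an acuity cut does so only by proxy.

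**The size is assumed, and no stated decision turns on it.** This stands. The design is a single observational cohort with no comparator and no UCVA threshold. At a stricter UCVA cut p is lower, so the absolute shift, p × f/(1 − f), is smaller. At p = 80% and f = 5% the shift is just inside the confidence half-width. The oblique shortfall disappears if enough second eyes are enrolled.

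**Reporting and timing are minor.** Only one post-operative visit is scheduled, so final BCVA most naturally means month 1, and it can come from the manifest refraction. A flow diagram is planned that could show the excluded eyes. These are missing details, and the main point does not depend on them.

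**Conclusion.** The concern holds and should be fixed. As written, the plan conditions every analysis on a post-operative outcome.

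For UCVA the direction is certain, given only that uncorrected acuity does not exceed best-corrected acuity. The size is unknown: over the ranges assumed here it runs from 1.2 points (p = 60%, f = 2%) to 8.9 points (p = 80%, f = 10%), and it is small if few eyes miss 20/40. The complication rate can be understated, but only if complicated eyes are excluded more often than others. For keratometry the harm shown is lost data and a narrower population, not a biased nomogram.

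**What to change.** Replace the exclusion sentence in section 8.3 with text such as:

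> AK complications are reported for all operated eyes, stating the number not assessed at month 1. Keratometric and nomogram analyses include all eyes with a usable biometer reading, and UCVA is reported for all eyes with a UCVA measurement, regardless of final BCVA. An analysis limited to eyes with month-1 BCVA (from the manifest refraction) of 20/40 or better is a labelled sensitivity analysis, with the number and cause of excluded eyes reported.

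Define a usable reading by a measurement-quality criterion fixed before the outcome data are examined. Name BCVA among the month-1 measurements in section 7.2.4, and add the eyes below 20/40 to the disposition diagram in section 3.3.2.

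The cost is a replaced sentence with its definition, one named measurement and one line in the diagram. Manifest refraction is already collected, so no visit is added. The downside is that UCVA may look slightly less favourable and will include some eyes limited by non-corneal disease; the sensitivity analysis shows how much that matters.
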